### 4.8.1 Additional Data Collection

We will ask each dialysis centre (both intervention and control centres) to send additional data from 15 random patients (no patient identifiers will be requested) including pre-dialysis patient temperatures, pre-dialysis systolic and diastolic blood pressure, the temperature of the dialysate, and the nadir systolic with its accompanying diastolic blood pressure. To ascertain baseline information, we will request this data be sent monthly starting as early as October 2015 until March 2017.

Beginning April 2017, we will ask each centre to send weekly reports for the first month of the trial, bi-weekly for the second month, and monthly thereafter. All of these data elements are available in the patient's dialysis run sheet as part of routine care. These data will allow us to assess adherence to the treatment allocation, and assess differences in average dialysis temperature and blood pressure between the two groups of dialysis centres.

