### **Methods**

#### **Study Design and Overview**

The Major outcomes with personalized dialysate *TEMP*erature (MyTEMP) is a pragmatic, 2-arm, parallel-group, registry-based, open-label, cluster RCT. The trial started on April 3, 2017, and enrolled 84 (of the 97) hemodialysis centers in Ontario, Canada, at that time. This province-wide trial is embedded into routine care with center-wide implementation of the intervention delivered by dialysis unit personnel rather than research staff (Supplemental Appendix 1—Section 1.7). Patient characteristics and outcomes will be largely obtained from administrative health care databases. This pragmatic design allows broad inclusion of dialysis centers and a large representative sample of patients that should yield highly generalizable findings (Figure 1).

Hemodialysis centers were randomized (1:1) to provide (1) a personalized temperature-reduced dialysate protocol (see “Intervention” section) or (2) a standard dialysate temperature of 36.5°C, which reflects usual practice at Ontario hemodialysis centers. Randomization with concealed allocation was conducted centrally on February 1, 2017, and centers were notified of their group allocation by the study team 2 months before the intervention start date. The primary outcome is a composite of cardiovascular-related death or hospital admission with myocardial infarction, congestive heart

**Figure 1.** Precis-2 wheel highlighting the pragmatism of MyTEMP trial for 9 domains.

Note. Small reductions in pragmatism relate to (1) monthly data collection from centers to assess intervention adherence and (2) contact with centers that had less than 80% adherence. MyTEMP = Major Outcomes with Personalized Dialysate TEMPerature.

failure, or ischemic stroke. Follow-up for study outcomes will continue until March 31, 2021.

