ICES. ICES is a prescribed entity for the purposes of Section 45 Ontario's Personal Health Information Privacy Act, which means that health information custodians, including physicians, hospitals, or long-term care homes, are permitted to disclose personal health information about their patients to ICES without patient consent. Secure access to these data is governed by policies and procedures that are approved by the Information and Privacy Commissioner of Ontario. These data sets will be linked using unique encoded identifiers and analyzed at ICES. More information about the databases and variables that will be used in this study is provided in Supplemental Appendices 6 and 7.

The following data, collected as part of routine care, will be obtained from the hemodialysis run sheet as part of patients' medical record: the patient's predialysis body temperature (measured as described in the "Intervention" section), the patient's predialysis systolic and diastolic blood pressure (typically measured while seated), the patient's nadir systolic with accompanying diastolic blood pressure during the hemodialysis session, and the prescribed dialysate temperature. Baseline data on these variables will be obtained from a random sample of 15 hemodialysis sessions from each center during the 2-month period before the intervention start date. After the intervention start date, these data will be collected from a random sample of 15 hemodialysis sessions weekly for the first month, biweekly for the second month, and monthly thereafter. Data will be collected on either the last Friday or Saturday of the data collection period. During the 4-year study follow-up, we expect to sample approximately 65 500 of 4.2 million hemodialysis sessions (Table 2).

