#### **1.4 What is the dialysate temperature used in current practice?**

Currently, the dialysate temperature used in most centres in Canada and the United States ranges from 36.5 °C to 36.7 °C (97.7°F to 98.1°F). In preparation for the MyTEMP trial, we collected data on the prescribed dialysate temperature and patients' pre-dialysis body temperatures for 12,012 hemodialysis sessions across 68 unique hemodialysis centres in Ontario over a six-month period (September 2016 to March 2017). Results are reported as the median (25th, 75th percentile). We confirmed the delivered dialysis temperature during this period was fixed for each dialysis session except for 5 of the 68 hemodialysis centres that used blood temperature monitoring. The prescribed dialysate temperature was 36.5 °C or 97.7 °F (36 °C [96.8 °F], 36.5 °C [97.7 °F]). The pre-dialysis body temperature was 36.3 °C or 97.3 °F (35.9 °C [96.6 °F], 36.6 °C [97.9 °F]) and 59% of hemodialysis sessions started with a pre-dialysis body temperature (measured using oral or tympanic instruments) less than 36.5 °C (97.7 °F). The difference between the pre-dialysis body temperature and prescribed dialysate temperature was 0.0 °C (0.3 °C lower, 0.4 °C higher than body temperature).

In the United States, it has been estimated that the average delivered dialysate temperature is 36.7 °C (98.1 °F). The prescribed dialysate temperature of 36.5 °C (97.7 °F) used by most nephrologists comes

from clinical tradition rather than empirical evidence; with the historic rationale that dialysate temperature should be similar to typical body temperature.

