Depression*	CIHI/ODB/OHIP
Diabetes mellitus	ORRS/CIHI-DAD/OHIP
Fracture	CIHI-DAD/OHIP
Heart failure ++	CIHI-DAD
Hemorrhage	OHIP/CIHI-DAD
Hypertension	ORRS/ CIHI-DAD/OHIP
Hypotension	CIHI-DAD
Ischemic Stroke ++	CIHI-DAD
Liver Disease	ORRS/ CIHI-DAD/OHIP

Lung disease (COPD)	ORRS/ CIHI-DAD/OHIP
Malignancy	ORRS /CIHI-DAD/OHIP
Myocardial infarction ++	ORRS/ CIHI-DAD
Other serious illness that would shorten life expectancy less than 5 years	ORRS
Peripheral vascular disease	ORRS/ CIHI-DAD/OHIP
Smoking	ORRS
Stroke/Transient ischemic attack	ORRS/CIHI-DAD
Subarachnoid Hemorrhage	CIHI-DAD
Syncope	CIHI-DAD
Drugs (for 65+ years)	
ACE Inhibitors	ODB
ARB	ODB
Anti-depressants	ODB
Anti-Psychotics	ODB
Benzodiazepine	ODB
Beta-Blockers	ODB
Healthcare Utilization	
Long term care facility utilization	ODB/OHIP/CCRS
Number of nephrology consults in the last 12 months	OHIP
Number of Family Doctor consults in the last 12 months	OHIP
Number of Hospitalizations in last 12 months	CIHII-DAD
Number of Visits to Emergency Department in last 12 months	NACRS
Total Healthcare Costs in last 12 months	Various sources at ICES 
Lab Data (Last measured)	
Hemoglobin	ORRS/OLIS
Urea	ORRS/OLIS
eGFR	ORRS/OLIS
Serum Albumin	ORRS/OLIS
Procedures / Monitoring	
Carotid endarterectomy	OHIP
Coronary angiogram	OHIP/CIHI-DAD
Coronary revascularization	OHIP/CIHI-DAD
Echocardiography	OHIP/CIHI-DAD
Holter monitoring	OHIP/CIHI-DAD

Other Variables	
Dialysate Temperature (baseline)	Case Report Forms**
Pre-dialysis systolic blood Pressure (baseline)	Case Report Forms**
Pre-dialysis diastolic blood pressure (baseline)	Case Report Forms**
Mean intra-dialytic nadir systolic blood pressure (baseline)	Case Report Forms**
Diastolic blood pressure accompanying the intra-dialytic nadir systolic blood pressure (baseline)	Case Report Forms**
Date of first nephrology visit	ORRS
Height	ORRS
Last measure weight	ORRS
Body Mass Index (BMI)	ORRS
History of Renal Transplant	ORRS /CIHI-DAD/OHIP
First Dialysis Modality	
Peritoneal Dialysis	ORRS/CORR
Hemodialysis	ORRS/CORR
Had a late nephrology referral	ORRS/CORR
Vascular access used at index date (April 01, 2017)	
Arteriovenous fistula	ORRS/CORR
Arteriovenous graft	ORRS/CORR
Central venous catheter	ORRS/CORR
Hemodialysis Characteristics at Index Date	
Patients Dialyzing in an Acute Care Hospital	ORRS
Patients Dialyzing in a Chronic or Community Hospital	ORRS
Duration of all dialysis modalities (Months)	ORRS

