**Analysis plan:** The primary analysis will follow an intent-to-treat approach. The primary outcome will be analyzed at the patient level as the hazard ratio of time-to-first event, estimated from a subdistribution hazards model. Within-center correlation will be accounted for using a robust sandwich estimator. In the primary analysis, patients’ observation time will end if they experience the primary outcome, emigrate from Ontario, or die of a noncardiovascular cause (which will be treated as a competing risk event). The between-group difference in the mean drop in intradialytic systolic blood pressure obtained during the dialysis sessions throughout the trial period will be analyzed at the center level using an unadjusted random-effects linear mixed model.

**Trial status:** The MyTEMP trial period is April 3, 2017, to March 31, 2021. We expect to analyze and report results by 2023 once the updated data are available at ICES.

**Trial registration:** MyTEMP is registered with the US National Institutes of Health at [clinicaltrials.gov](https://clinicaltrials.gov) (NCT02628366).

**Statistical analytic plan:** Version 1.1 June 15, 2021.

Creative Commons Non Commercial CC BY-NC: This article is distributed under the terms of the Creative Commons Attribution-NonCommercial 4.0 License (<https://creativecommons.org/licenses/by-nc/4.0/>) which permits non-commercial use, reproduction and distribution of the work without further permission provided the original work is attributed as specified on the SAGE and Open Access pages (<https://us.sagepub.com/en-us/nam/open-access-at-sage>).

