### Analysis

#### Outcome Definitions

The *primary outcome* is a composite of cardiovascular-related death or hospital admission with myocardial infarction, congestive heart failure, or ischemic stroke. Cardiovascular-related hospitalization will be defined using main diagnostic codes from CIHI-DAD. Data on cause of death will be obtained from the ORGD, which uses a modified version of Becker's groupings based on *International Classification of Diseases 10th Revision (ICD-10)* coding. The specific algorithm for the primary composite outcome is provided in the trial protocol.

The *key secondary outcome* is the mean drop in intradialytic systolic blood pressure. To calculate this, we will subtract each patient's nadir intradialytic systolic blood pressure from their predialysis systolic blood pressure, and then average these values at the center level for each of the 48 timepoints during the 4-year trial period. As described in section "Timing of Outcome Assessments" above, anonymized data on patients' predialysis systolic blood pressure and their intradialytic systolic blood pressure were collected from a random sample of 15 patients at monthly intervals from each dialysis center. These blood pressure data will be averaged monthly for each center. As such, during the 4-year trial period, we will have a total of 48 summary measures (ie, 1 a month), for each of the 84 centers in our trial.

The *other secondary outcomes* are a composite of all-cause mortality or cardiovascular-related hospitalization, all cause-mortality, and the components of the primary outcome examined separately: hospital admission with myocardial infarction, hospital admission with congestive heart failure, hospital admission with ischemic stroke, and cardiovascular-related mortality.

We will also examine a composite of all-cause emergency room visits or all-cause hospitalizations (each will also be examined separately as the number of visits and hospitalizations, respectively), a hospital encounter with lower limb amputation, and a hospital encounter with a major fall or fracture.

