We will explore a range of prior distributions (see Appendix 1 and Table 1 in the Supplemental Material) that can condition the posterior distribution. We will use priors to reflect varying degrees of enthusiasm and skepticism for the benefit of a personalized temperature-reduced dialysate before starting MyTEMP. The parameter's estimate and standard errors will be obtained from the analysis (as described in the "Analysis of the primary outcome" section above) and combined with prior distributions to obtain the model's posterior distributions. We will estimate the Bayes factor and credible intervals using Markov chain Monte Carlo sampling techniques with at least 3 parallel chains. We will report the probability of the truth of our conclusions. This approach enables the specification of prior information, controls the sampling, and obtains posterior summary statistics and convergence diagnostics. The convergence of the generated Markov chain will be assessed by examining the trace plot, autocorrelation function plot, and posterior density plot.

**Analysis of the key secondary outcome.** The between-group difference in the key secondary outcome (the mean drop in patients' intradialytic systolic blood pressure) will be obtained using an unadjusted, generalized linear mixed model on the cluster-period summaries that accounts for the repeated measurements at the cluster level over time using longitudinal analysis methods, and appropriate CIs will be generated as described in section "Confidence Intervals and *P* Values: Level of Statistical Significance" in the "Statistical Principles" section above.

**Analysis of other secondary outcomes.** We will use the same analytic approach as for the primary outcome to examine each component of the primary outcome separately and the other secondary time-to-event outcomes (ie, see secondary outcomes listed in "Confidence Intervals and *P* Values: Level of Statistical Significance" and "Outcome Definitions" sections). Death (or noncardiovascular-related death) will be treated as a competing-risk event in these analyses when not part of the outcome. The model assumptions will be assessed as described in the "Analysis of the primary outcome" section, above.

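### The key secondary blood-pressure model omits each centre's planned pre-intervention value without giving a reason, so a valid test gives up precision

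*Combined protocol and SAP*

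**What the plan says.** The SAP section on analysis of the key secondary outcome states that the between-group difference "will be obtained using an unadjusted, generalized linear mixed model on the cluster-period summaries". The SAP abstract agrees: the outcome "will be analyzed at the center level using an unadjusted random-effects linear mixed model". Under Outcome Definitions, the data are centre means from the trial period only: "we will have a total of 48 summary measures" per centre, one a month.

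The final protocol plans a baseline for the same measure. Its Data Collection section lists pre-dialysis and nadir systolic pressure among the run-sheet items and says baseline data will come "from a random sample of 15 hemodialysis sessions from each center during the 2-month period before the intervention start date". Appendix 7 of the final protocol lists both pressures as baseline variables, and the SAP refers to that appendix for baseline characteristics. The original protocol, section 4.8.1, asked for the same items before the trial: "we will request this data be sent monthly starting as early as October 2015 until March 2017".

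Neither the protocol, the SAP, the change table nor the corrigendum explains why the model is unadjusted. The change table discusses only weighting by cluster size. The primary analysis, by contrast, adjusts for the constrained covariates and for each centre's historical rate of the primary composite.

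**The concern.** The mean systolic drop is the trial's test of mechanism. It is tested at two-sided 0.01 with a 99% interval, and it is one of two gates to the remaining secondary outcomes. If the primary outcome is not significant, this test alone decides whether the six ordered secondary tests go ahead.

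The plan's power calculation assumes that repeated summaries from one centre correlate at 0.4. On that assumption, a centre's pre-trial drop predicts its in-trial drop. If the baseline is left out, stable differences between centres stay in the error term and widen the interval. The plan uses centre history for the primary outcome but not here, where a directly matching baseline is planned.

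**Working it through.** **Inputs.** From the final protocol, Statistical Power section and Appendix 11c: SD of centre-period means 7.2 mm Hg, constant ICC 0.4, at least 6 repeated observations, 84 centres (42 per arm), two-sided alpha 0.01, and a stated 84% power for 4 mm Hg. From the SAP: T = 48 summaries per centre.

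**Reproducing the stated power (unadjusted, T = 6).**
- Variance of a centre's follow-up mean: V = 7.2² × [ICC + (1 − ICC)/T] = 51.84 × (0.4 + 0.6/6) = 25.92, so its SD is 5.09.
- SE of the arm difference = √(2 × 25.92/42) = 1.11 mm Hg.
- Power for 4 mm Hg is 84.7% by the normal approximation and 82.9% by noncentral t with 82 df. Both fit the stated 84%.

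**Adding one baseline summary per centre**, with the same SD and ICC as a follow-up month:
- Squared correlation of the baseline with the follow-up mean: r² = ICC²/[ICC + (1 − ICC)/T].
- T = 6: 0.16/0.50 = 0.320. T = 48: 0.16/0.4125 = 0.388.
- Adjusted SE = unadjusted SE × √(1 − r²).
- Detectable difference at 80% power = (2.576 + 0.842) × SE.

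| ICC 0.4, all 84 centres | T = 6 | T = 48 |
|---|---|---|
| SE, unadjusted → adjusted (mm Hg) | 1.11 → 0.92 | 1.01 → 0.79 |
| Variance reduction | 32% | 39% |
| 99% CI half-width (mm Hg) | 2.86 → 2.36 | 2.60 → 2.03 |
| Detectable at 80% power (mm Hg) | 3.8 → 3.1 | 3.4 → 2.7 |
| Power for 4 mm Hg | 85% → 96% | 92% → 99% |
| Power for 3 mm Hg | 55% → 76% | 65% → 89% |

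A simulation of 10,000 trials per scenario agreed. Power for 4 mm Hg was 82.9% → 95.3% (T = 6) and 90.3% → 99.1% (T = 48). Type I error stayed near 0.01 for both models (0.9% and 0.8% at T = 6; 1.3% and 1.1% at T = 48).

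**Incomplete baseline.** The only pre-trial collection reported covers 68 centres. Assuming 34 per arm with a baseline and 8 per arm without, generalized least squares with a common baseline mean gives an SE of 0.95 (T = 6, variance −28%) or 0.82 (T = 48, variance −34%). Detectable differences are 3.2 and 2.8 mm Hg.

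**Weaker correlation.**
- Constant ICC 0.2: r² = 0.120 (T = 6) or 0.185 (T = 48), and the variance cut is 10% or 15% with 68 centres. The unadjusted SE is then already 0.91 or 0.73.
- Correlation 0.4 × d^lag, lag in months, T = 48: r² = 0.281, 0.157 and 0.097 for d = 0.99, 0.97 and 0.95. Power for 4 mm Hg goes from 95.5% to 99.3%, 98.9% to 99.7%, and 99.8% to 99.9%. The interval narrows by 15%, 8% and 5%.

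**Risk from a contaminated baseline.** The covariate slope is ICC × 7.2²/7.2² = 0.4. If a fraction f of intervention centres already showed the full effect at baseline, the estimate shrinks by 0.4 × f. That is 4% at f = 10% (0.16 of 4 mm Hg) and 10% at f = 25% (0.4 of 4 mm Hg).

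**The case against.** The strongest reply is that this refines a valid analysis. The unadjusted test is unbiased and meets its stated power, and no passage contradicts another. The planned analysis uses 48 summaries, so the relevant power gain for 4 mm Hg is 92% to 99%; the 85% to 96% comparison belongs to the 6-summary planning case. The protocol calls the ICC of 0.4 conservative. If it was set high for safety, the true correlation is lower, the baseline explains less, and the unadjusted test is already stronger. All of this stands, and it limits the size of the gain. It does not change its direction: precision improves in every case tried.

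The second reply is timing. The final protocol says "centers were notified of their group allocation by the study team 2 months before the intervention start date", so the planned baseline window opens after centres knew their arm and were preparing for it. In an open-label trial that is a fair reason for caution, because adjusting for an affected baseline would pull the estimate toward zero. The documents neither show nor rule out early uptake. This stands as a real but small risk, sized above, and the choice of samples and a by-arm check address it.

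The third reply is availability. The baseline is a plan; the SAP describes blood-pressure collection only during the trial. The pre-trial data actually reported, "12,012 hemodialysis sessions across 68 unique hemodialysis centres in Ontario over a six-month period", describe temperatures and not pressures. This also stands, and the number of usable baselines must be confirmed.

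**Conclusion.** The concern holds. The key secondary model leaves out a planned and probably informative baseline and gives no reason. The cost is precision only: validity and the stated 84% power are unaffected, and the primary outcome is untouched. With the SAP's 48 summaries and the plan's SD and constant ICC, the avoidable variance is about 39%, or 34% if only 68 centres have a baseline. The practical benefit is a narrower 99% interval and better power for effects below the design value, for example 65% to 89% at 3 mm Hg. These sizes rest on the baseline behaving like one follow-up month and on a correlation of 0.4. With an ICC of 0.2 or fading correlation the variance cut is roughly 10% to 28%, and little power for 4 mm Hg is left to recover. The change should be made. Confidence in the size of the gain is medium, because the true correlation and the completeness of the baseline are not documented.

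**What to change.** Before outcome data are seen, amend the SAP as follows:

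- Pre-specify each centre's pre-intervention mean systolic drop as a covariate. Alternatively, enter the pre-trial summaries as an outcome period with a common mean across arms. The second form keeps centres without a baseline and needs no missing-data indicator.
- Prefer samples taken before allocation was disclosed (before February 2017) where they exist. If February–March 2017 samples are used, say that they post-date allocation, and check that baseline drop and dialysate temperature do not already differ by arm.
- Treat the centre-level intradialytic hypotension proportions the same way.
- Report the unadjusted model as supportive.
- If the baseline is still to be left out, state why.

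The cost is one or two sentences in the SAP, about one degree of freedom, and no new data if the planned samples were taken. The remaining risks are missing baselines and the small attenuation from early uptake.

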Centre Factors	
Number of patients at centre	ORRS
Centre Transplant Rate in previous 24 months	ORRS /CIHI-DAD/OHIP
Centre Death Rate in previous 24 months	ORRS/RPDB
Centre Transfer rate in previous 24 months	ORRS
Number of stations within centre	ORRS
Centre uses electronic dialysis run sheets	Case Report Forms**
Centre uses tympanic temperature measurement	Case Report Forms**
Centre uses heated chairs	Case Report Forms**

ODB= Ontario Drug Benefit database contains claims for prescription drugs received under the Ontario Drug Benefit program. Most are for those >=65 but from 1997 forward we also have data on other ODB program; OLIS=

Ontario Laboratories Information System; ORRS=Ontario Renal Reporting System has information is a database of all pre-dialysis, acute dialysis and chronic dialysis patients in Ontario since 2010; CIHI-DAD= Discharge Abstract Database records detailed diagnosis and procedural information on all hospitalizations in Ontario. Up to 25 unique diagnostic and 20 procedural codes can be assigned to each hospitalization.; OHIP= Ontario Health Insurance Plan database contains health claims for inpatient and outpatient physician services;

\* Depression is defined as (1) having two events of OHIP diagnosis, hospitalizations, or ODB drug prescription; or (2) having at least one event in at least two of OHIP diagnosis, hospitalizations, or ODB drug prescription.

\*\*This information is captured on the dialysis run sheet that is completed with every dialysis treatment in Ontario (i.e. centres do not have to collect additional data outside standard of care).

++ History of components of primary or secondary outcomes

**Appendix 8:** Algorithm for capturing primary composite outcome

Outcome	Algorithm	Position of code	Performance
Cardiovascular-related death ▲, ¥	ORGD: Leading Cause of Death LCD_33 = Chronic rheumatic heart disease LCD_34 = Hypertensive disease LCD_35 = Ischemic heart disease LCD_36 = Pulmonary heart disease and related LCD_37 = Nonrheumatic valve disorders LCD_38 = Cardiomyopathy LCD_39 = Cardiac arrest LCD_40 = Cardiac arrhythmias LCD_41 = Heart failure and complications, ill-defined heart disease LCD_42 = Cerebrovascular diseases LCD_43 = Atherosclerosis LCD_44 = Aortic aneurysm and dissection	N/A	Not available

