We will assess the intervention's effect on the rate of the primary outcome using the multivariable generalized-estimating-equations extension for the Fine and Gray's subdistribution proportional hazards, with an exchangeable covariance matrix, to account for the clustering of patients within hemodialysis centers and the competing risk of noncardiovascular death. We will supplement the primary analysis with the cause-specific hazard model for both the primary outcome and competing-risk of noncardiovascular death. We also will explore the composite of our primary event with the competing risk as described in the "Additional Analyses" section below.

As our study used covariate-constrained randomization, we will adjust for constrained covariates in our analyses; these patient-level covariates include age, biological sex, rural status, race, modified Charlson comorbidity index, number of unique hospital admissions (in the 12 months before the index date), number of unique hypertensive prescriptions, referral to a nephrologist  $< 3$  months before initiating dialysis, type of vascular access on the index date, serum albumin on the index date, and the following baseline comorbidities: myocardial infarction, congestive heart failure, peripheral vascular disease, and diabetes mellitus. We will also adjust for the cluster-level historical rate of the composite outcome of cardiovascular-related death and major cardiovascular-related hospitalization.

We will evaluate and report the model assumptions for the clustered subdistribution hazard and cause-specific hazards models. Appropriate techniques will be applied when model assumptions are violated. Specifically, this model assumes a linear relationship between the log hazard and covariates. We will assess the assumption for linearity using residual plots. From historic data, we expect that the linearity assumption will be violated for our continuous covariates. If this occurs, we plan to correct for the nonlinear covariates using restricted cubic splines. We will assess the proportionality of the hazard visually and use the Schoenfeld test for the intervention. If the assumption of proportionality is violated, we will consider alternative methods so that the model remains valid (ie, a time-stratified model to identify constant hazard ratios within appropriate time intervals).

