The number of all-cause hospital admissions and emergency department visits during the study period will be analyzed using a negative binomial model relevant for count data while adjusting for clustering of dialysis centers with generalized estimating equations and using the log of time as an offset. We have chosen a negative binomial model because the historic data show a propensity for overdispersion (ie, the mean and variance of all-cause hospitalization and emergency room visits appear to be different). We will assess model assumptions and evaluate the fit of our model. From historic data, we expect that 85% of our cohort will have at least 1 hospital admission and/or emergency department visit in follow-up, and we also expect this outcome to be right skewed. We will perform and report model diagnostics.

The four definitions of intradialytic hypotension will be analyzed at the center level in a similar manner as the key secondary outcome (ie, unadjusted, generalized linear mixed model on the cluster-period summaries).

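### The all-cause mortality models adjust for each centre's cardiovascular history but not its pre-trial death rate, forgoing a modest, assumption-dependent gain in precision

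*Combined protocol and SAP*

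**What the plan says.** The SAP's paragraph on the remaining secondary endpoints, within Analytic Methods, states: "We will use the same analytic approach as for the primary outcome to examine each component of the primary outcome separately". The same sentence extends this to the other secondary time-to-event outcomes. With the ordered list under Confidence Intervals and P Values, that makes six: the composite of all-cause mortality or cardiovascular hospitalization, all-cause mortality, myocardial infarction, heart failure, ischemic stroke and cardiovascular death. The first two are also first in the testing order.

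The primary model adjusts for the patient-level covariates used to constrain the randomization, and then: "We will also adjust for the cluster-level historical rate of the composite outcome of cardiovascular-related death and major cardiovascular-related hospitalization". No other centre-level covariate is named, and no outcome-specific centre rate is named for any secondary outcome.

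The final protocol's Appendix 7, under Centre Factors, lists "Centre Death Rate in previous 24 months" among the baseline variables.

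The key secondary outcome (drop in systolic pressure) is handled differently, by an "unadjusted, generalized linear mixed model on the cluster-period summaries".

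**The concern.** Adjusting the primary outcome for its own centre history is sensible. Carried over to all-cause mortality, the same covariate fits less well, because it contains no deaths from sepsis, malignancy and other non-cardiovascular causes, which appear to be most deaths in this population. Centres with high overall mortality need not be those with high cardiovascular composite rates. Differences between centres in death rate that the composite history does not capture stay in the error term, and with 84 centres that widens the confidence interval.

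The variable best matched to the outcome is already on the baseline list. At stake is some precision for the two outcomes that head the secondary testing sequence.

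**Working it through.** **1. The plan's own figure.** Final protocol, Statistical Power: rate 0.095 per person-year, CV 0.216, harmonic mean 163 person-years per centre, 42 centres per arm, HR 0.80 (so 0.076 in the intervention arm), two-sided alpha 0.04 (z = 2.054). With the Hayes–Moulton formula,

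power = Φ( √[ (c − 1)(λ0 − λ1)² / { (λ0 + λ1)/y + k²(λ0² + λ1²) } ] − z )

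= Φ( √[ 41 × 0.019² / (0.001049 + 0.000691) ] − 2.054 ) = Φ(2.917 − 2.054) = 80.6%.

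Using c in place of c − 1 gives 81.6%. The stated 80% reproduces, so these inputs are a sound base.

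**2. A death rate.** No all-cause rate is stated. The SAP supplement (text after the Figure 2 legend) expects 21% of patients to have the primary composite and 23% to die of non-cardiovascular causes. Scaling: 0.095 × 23/21 = 0.104 non-cardiovascular deaths per person-year. Adding cardiovascular death at 0.031 (protocol Appendix 9) gives 0.135. Non-cardiovascular share: 0.104/0.135 = 77%.

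**3. Model for the gain.** For a centre with y person-years, the variance of the log death rate is k²(1 − R²) + 1/(λy), where R² is the share of between-centre variance that the history covariates explain. Let s be the stability of centre effects over time and r the correlation of death and composite effects between centres.

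- Reliability of a measured history = k²/(k² + 1/(λ × history person-years)).
- R² for death history = s² × its reliability.
- R² for composite history = (s·r)² × its reliability.
- Correlation of the two measured histories = r × √(product of reliabilities).
- R² for both follows from the usual two-predictor formula.

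Assumed: k 0.10–0.216, s 0.6–0.8, r 0.3–0.7, death history over half of y (24 months), composite history over y (4 years) with its CV of 0.216.

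**4. One case in full:** k = 0.216, y = 163, s = 0.7, r = 0.5.

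- Reliability, deaths: 0.04666/(0.04666 + 1/(0.135 × 81.5)) = 0.339. Reliability, composite: 0.04666/(0.04666 + 1/(0.095 × 163)) = 0.419.
- R²: deaths 0.49 × 0.339 = 0.166; composite 0.1225 × 0.419 = 0.051; correlation 0.5 × √(0.339 × 0.419) = 0.189; both 0.189.
- Composite history only: √(0.04666 × 0.949 + 0.04544) = 0.2995. Both: √(0.04666 × 0.811 + 0.04544) = 0.2885.
- Reduction: 1 − 0.2885/0.2995 = 3.7%.

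**5. Range of the reduction in standard error, all-cause mortality, death history added.**

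| Between-centre CV of mortality | y = 163 (harmonic mean) | y = 258 (median) |
|---|---|---|
| 0.10 | 0.2–0.5% | 0.4–1.1% |
| 0.15 | 0.8–2.0% | 1.4–3.8% |
| 0.216 | 2.2–5.4% | 3.3–8.8% |

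**6. The single components.** At 163 person-years, the protocol's rates give about 5 historical events per centre for myocardial infarction, heart failure or cardiovascular death (0.030–0.032 × 163) and about 2 for stroke (0.012 × 163). At CV 0.216 the reliability of an own-history rate is 0.04–0.20, against 0.42 for the composite history. Adding it gains 0–1.8% (stroke at most 0.3%); replacing the composite history with it changes the standard error by between −1.0% and +1.6% (positive is a reduction).

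**The case against.** The SAP gives a reason for its covariates: they are the ones that constrained the randomization. Adjusting for those is principled, and leaving out a further prognostic variable is neither an error nor a bias. That stands.

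The size of the gain also rests on quantities the documents do not give: the between-centre CV of mortality, its stability over time and its correlation with the composite history. The calculation takes no account of the patient-level covariates already in the model (age, comorbidity index, albumin, vascular access and others), which absorb some case-mix differences between centres. The 77% share is constructed, and the corrigendum now counts many out-of-hospital deaths as cardiovascular, so the share under the governing definition is unknown. These points stand; they make the gain conditional.

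Several stronger readings are tempting but unsupported:

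- A reader might infer that every secondary outcome is affected. The key secondary outcome and the intradialytic hypotension outcomes are explicitly unadjusted, and the count outcomes have their own model ("negative binomial model relevant for count data while adjusting for clustering of dialysis centers with generalized estimating equations").
- A reader might infer that between-centre variation dominates the standard error. For all-cause death at 163 person-years, sampling variance is 1/(0.135 × 163) = 0.045, against between-centre variance of 0.0225 at CV 0.15 and 0.047 at 0.216: smaller, then about equal. For myocardial infarction, sampling variance is about 0.20.
- A reader might extend the remedy to each component's own history. Step 6 shows almost nothing to gain.
- A reader might want each patient's prior-year emergency visits in the count model. For patients entering after the start, the index date falls when the 90-day stability rule is met, so that look-back takes in about 90 days on the allocated protocol.

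**Conclusion.** The point holds in a narrow form. The models for all-cause mortality and for the composite containing it use a centre-level covariate that omits non-cardiovascular death, although a better-matched baseline variable is already listed. The consequence is lost precision, not bias.

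For all-cause mortality the loss is about 1% or less of the standard error at a between-centre CV of 0.10, 1–4% at 0.15 and 2–9% at 0.216. This assumes a death rate of 0.135 per person-year, stability 0.6–0.8, correlation 0.3–0.7 and 163–258 person-years per centre, before allowing for what the patient-level covariates explain. For the mortality composite the gain should be smaller, because roughly half of its first events are already in the cardiovascular composite; it was not computed. This is a worthwhile improvement, not a defect that threatens any conclusion.

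**What to change.** Keep all constrained covariates and the composite history. Before outcome data are viewed, add one sentence to the SAP's Analysis of other secondary outcomes: the models for all-cause mortality and for the composite of all-cause mortality or cardiovascular hospitalization will also include the centre's 24-month death rate. State that its window ends before the trial start on April 3, 2017, because Appendix 7 does not say what date the 24 months run back from, and the covariate must not be open to influence by treatment. Leave the models for myocardial infarction, heart failure, stroke and cardiovascular death as they are.

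The cost is one degree of freedom among 84 clusters and no new data collection. Timing matters: added after outcomes are seen, the term would look data-driven.
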